6.2. Study Population

Patients with metastatic (Group 1) or unresectable locally advanced (Group 2) BCC who experienced progression of disease on HHI therapy, or were intolerant of prior HHI therapy.

6.2.1. Inclusion Criteria

A patient must meet the following criteria to be eligible for inclusion in the study:

1. Histologically confirmed diagnosis of invasive BCC
Note for clarification: The following are acceptable histologic subtypes of BCC: nodular, morpheaform, metatypical, superficial, micronodular, infiltrative, mixed, basosquamous, keratotic, desmoplastic
2. Patients must be deemed unlikely to benefit from further therapy with an HHI due to any of the following:
 - a. Prior progression of disease on HHI therapy, or
 - b. Intolerance of prior HHI therapy defined as:
 - (i) any Grade 3 or 4 AE deemed related to HHI
 - (ii) Or any of the following HHI-related events in patients with at least 3 months of exposure to HHI therapy (exclusive of treatment breaks):
 - Grade 2 muscle spasms or myalgias (iia)
 - Grade 2 dysgeusia or anorexia, if accompanied by \geq Grade 1 weight loss (iib)
 - Grade 2 nausea or diarrhea despite medical management or (iic)
 - c. No better than a stable disease after 9 months on HHI therapy (exclusive of treatment breaks)
3. At least 1 lesion that is measurable by study criteria

If a previously radiated lesion is to be followed as a target lesion, progression must be confirmed by biopsy after radiation therapy. Previously radiated lesions may be followed as non-target lesions if there is at least 1 other measurable target lesion.

Group 1: At baseline, there must be at least 1 measurable lesion \geq 10 mm in maximal diameter (1.5 cm in short axis for lymph nodes) according to RECIST 1.1 criteria

Group 2: At baseline, there must be at least 1 measurable baseline lesion in which the longest diameter and the perpendicular diameter are both ≥ 10 mm if measured by digital medical photography. Non-measurable disease for Group 2 is defined as either unidimensionally measurable lesions, tumors with margins that are not clearly defined, or lesions with maximum perpendicular diameters < 10 mm. Patients without measurable disease at baseline are not eligible for the study.

Note in clarification: In the case of a Group 1 patient with metastatic disease that does not meet target lesion criteria by RECIST 1.1 (eg, bone only lesions, perineural disease; [Appendix 1](#)) and with externally visible BCC target lesion(s), [Appendix 2](#) may be used, in which bi-dimensional measurements are required (at baseline, perpendicular diameters must both be ≥ 10 mm). The patient would then be enrolled in Group 1 with the plan to measure externally visible target lesion(s) by photography with bi-dimensional measurements. The metastatic lesions that are not measurable by RECIST 1.1 criteria would be followed as non-target lesions on scans.

In the case of a Group 2 patient with a deeply invasive lesion that the investigator deems is best measured by magnetic resonance imaging (MRI) or computed tomography (CT), measurement for that target lesion will be done according to RECIST 1.1 criteria ([Appendix 1](#)). The requirement for a lesion to be measurable by RECIST 1.1 is that it must be ≥ 10 mm in longest dimension.

4. Eastern Cooperative Oncology Group (ECOG) performance status ≤ 1
5. At least 18 years old
6. Hepatic function:
 - a. Total bilirubin ≤ 1.5 x upper limit of normal (ULN) (or ≤ 3 x ULN, if liver metastases). Patients with Gilbert's Disease and total bilirubin up to 3x ULN may be eligible after communication with and approval from the medical monitor
 - b. Transaminases ≤ 3 x ULN (or ≤ 5 x ULN, if liver metastases)
 - c. Alkaline phosphatase (ALP) ≤ 2.5 x ULN (or ≤ 5 x ULN, if liver or bone metastases)

Note for patients with hepatic metastases who wish to enroll in Group 1: If transaminase levels (AST and/or ALT) are > 3 x but ≤ 5 x ULN, total bilirubin must be ≤ 1.5 x ULN. If total bilirubin is > 1.5 x but ≤ 3 x ULN, both transaminases (AST and ALT) must be ≤ 3 x ULN.

7. Renal function: Serum creatinine ≤ 2 x ULN or estimated creatinine clearance > 35 mL/min (according the method of Cockcroft and Gault)
8. Creatine phosphokinase (CPK) (also known as CK [creatin kinase]) elevation \leq grade 2
9. Bone marrow function:
 - a. Hemoglobin ≥ 9.0 g/dL
 - b. Absolute neutrophil count (ANC) $\geq 1.5 \times 10^9/L$
 - c. Platelet count $\geq 75 \times 10^9/L$
10. Anticipated life expectancy > 12 weeks

11. All patients in either group must consent to provide archived or newly obtained tumor material (either formalin-fixed, paraffin-embedded [FFPE] block or 10 unstained or stained slides) for central pathology review for confirmation of diagnosis of BCC. This material must be confirmed as received by the central laboratory prior to enrollment.
12. **Group 2 only (unresectable locally advanced BCC):** Patients must consent to undergo biopsies of externally visible BCC lesions at baseline, cycle 1 day 22 (± 3 business days), at time of tumor progression, and at other time points that may be clinically indicated in the opinion of the investigator
13. Willing and able to comply with clinic visits and study-related procedures
14. Provide signed informed consent prior to any screening procedures (with the exception of brain MRI which is allowed to be obtained within 60 days of enrollment).
15. Group 2 only: Patients in Group 2 must be deemed to have unresectable disease. Surgery must be deemed contraindicated in the opinion of a Mohs dermatologic surgeon, a head and neck surgeon, or plastic surgeon. A copy of the surgeon's consultation note (surgeon may be site PI) from a clinical visit within 60 days of enrollment must be submitted.

Acceptable contraindications in the surgeon's note include:

- a. BCC that has recurred in the same location after 2 or more surgical procedures and curative resection is deemed unlikely
- b. BCCs with significant local invasion that precludes complete resection
- c. BCCs in anatomically challenging locations for which surgery may result in severe disfigurement or dysfunction (eg, removal of all or part of a facial structure, such as nose, ear, or eye; or requirement for limb amputation)

Other conditions deemed to be contraindicating for surgery must be discussed with the medical monitor before enrolling the patient.

16. **Group 2 Only:** Patients in Group 2 must be deemed as not appropriate for radiation therapy. Specifically, patients must meet at least 1 of the following criteria:
 - a. A patient previously received radiation therapy for BCC, such that further radiation therapy would exceed the threshold of acceptable cumulative dose, per the radiation oncologist. A copy of the radiation oncologist's consultation note, from a clinical visit within 60 days of enrollment, must be submitted.
 - b. Judgment of radiation oncologist that such tumor is unlikely to respond to therapy. A copy of the radiation oncologist's consultation note, from a clinical visit within 60 days of enrollment, must be submitted.
 - c. A clinic note from the investigator indicating that an individualized benefit:risk assessment was performed by a multidisciplinary team (consisting of, at minimum, a radiation oncologist AND EITHER a medical oncologist with expertise in cutaneous malignancies OR a dermato-oncologist, OR a head and neck surgeon) within 60 days prior to enrollment in the proposed study, and the radiation therapy was deemed to be contraindicated. Acceptable contraindications to radiation therapy in the investigator's note for patients who have not received any prior radiation include: BCCs in anatomically challenging locations for which radiation therapy would be

associated with unacceptable toxicity risk in the context of the patient's overall medical condition in the opinion of the multidisciplinary team (eg, a neck tumor for which radiation therapy would result in potential need for a percutaneous gastrostomy tube). A copy of the investigator's consultation note documenting the multidisciplinary assessment must be submitted.

6.2.2. Exclusion Criteria

A patient who meets any of the following criteria will be excluded from the study:

1. Ongoing or recent (within 5 years) evidence of significant autoimmune disease that required treatment with systemic immunosuppressive treatments, which may suggest risk for immune-related adverse events (irAEs). The following are not exclusionary: vitiligo, childhood asthma that has resolved, type 1 diabetes, residual hypothyroidism that required only hormone replacement, or psoriasis that does not require systemic treatment.
2. Prior treatment with an agent that blocks the PD-1/PD-L1 pathway
3. Prior treatment with other systemic immune-modulating agents within fewer than 28 days prior to the first dose of cemiplimab. Examples of immune-modulating agents include therapeutic vaccines, cytokine treatments, or agents that target cytotoxic T-lymphocyte antigen 4 (CTLA-4), 4-1BB (CD137), or OX-40.

Note in clarification: Prior treatment with imiquimod or other topical or intralesional immune modulators will not be exclusionary

4. Untreated brain metastasis(es) that may be considered active. (Note: patients with brain involvement of BCC due to direct extension of invading tumor, rather than metastasis, may be allowed to enroll if they do not require >10 mg prednisone daily, after discussion and approval of the medical monitor). Patients with previously treated brain metastases may participate provided that the lesion(s) is (are) stable (without evidence of progression for at least 6 weeks on imaging obtained in the screening period), and there is no evidence of new or enlarging brain metastases, and the patients do not require any immunosuppressive doses of systemic corticosteroids for management of brain metastasis(es) within 28 days of the first dose of cemiplimab.
5. Immunosuppressive corticosteroid doses (>10 mg prednisone daily or equivalent) within 4 weeks prior to the first dose of cemiplimab

Note: Patients who require brief courses of steroids (eg, as prophylaxis for imaging studies due to hypersensitivity to contrast agents) are not excluded

6. Active infection requiring therapy, including positive tests for human immunodeficiency virus (HIV)-1 or HIV-2 serum antibody, hepatitis B virus (HBV), or hepatitis C virus (HCV)
7. History of pneumonitis within the last 5 years
8. Any anticancer treatment other than radiation therapy (chemotherapy, targeted systemic therapy, imiquimod, photodynamic therapy), investigational or standard of care, within 30 days of the initial administration of cemiplimab or planned to occur during the study

period (patients receiving bisphosphonates or denosumab allowed because these are not considered anticancer treatments in this protocol)

Notes: (a) For patients with multiple BCCs at baseline that are not designated by the investigator as target lesions, treatment of these non-target BCCs with surgery may be permitted but must be discussed with the medical monitor prior to any surgical procedure. (b) Patients are excluded if they receive any radiation therapy within ≤ 14 days of the initial administration of cemiplimab or planned to occur during the study period.

9. History of documented allergic reactions or acute hypersensitivity reaction attributed to antibody treatments
10. Patients with allergy or hypersensitivity to cemiplimab or to any of the excipients must be excluded.
11. Concurrent malignancy other than BCC and/or history of malignancy other than BCC within 3 years of date of first planned dose of cemiplimab, except for tumors with negligible risk of metastasis or death, such as adequately treated CSCC of the skin, carcinoma in situ of the cervix, or ductal carcinoma in situ of the breast, or low-risk early stage prostate adenocarcinoma (T1-T2a N0M0 and Gleason score < 6 and PSA < 10 ng/mL) for which the management plan is active surveillance, or prostate adenocarcinoma with biochemical-only recurrence with documented PSA doubling time of > 12 months for which the management plan is active surveillance (D'Amico 2005, Pham 2016). Patients with hematologic malignancies (eg, chronic lymphocytic leukemia) are excluded.
12. Any acute or chronic psychiatric problems that, in the opinion of the investigator, make the patient ineligible for participation
13. Patients with a history of solid organ transplant (patients with prior corneal transplants may be allowed to enroll after discussion with and approval from the medical monitor)
14. Any medical co-morbidity, physical examination finding, or metabolic dysfunction, or clinical laboratory abnormality that, in the opinion of the investigator, renders the patient unsuitable for participation in a clinical trial due to high safety risks and/or potential to affect interpretation of results of the study

Note in clarification: For Group 2 patients, the investigator must contact the sponsor's medical monitor regarding any patients who the investigator feels cannot provide the required baseline tumor biopsies.

15. Inability to undergo any contrast-enhanced radiologic response assessment

Note regarding imaging options: A patient who is unable to undergo CT with iodinated contrast (eg, due to contrast allergy) would not be excluded if his/her disease can be measured by MRI with gadolinium. A patient who is unable to undergo MRI with gadolinium would not be excluded if his/her disease can be measured by CT scan with contrast.

Note regarding Group 2 patients: In selected cases, a patient in Group 2 who is unable to undergo any contrast enhanced radiographic imaging (neither CT with iodinated contrast nor MRI with gadolinium) may be eligible if the patient's disease can be

comprehensively assessed with digital medical photography, after communication with and approval from the medical monitor.

Note in clarification: For Group 2 patients, the investigator must contact the Sponsor's medical monitor regarding any patients that the investigator feels cannot provide the required baseline biopsies.

16. Breastfeeding
 17. Positive serum pregnancy test (a false positive pregnancy test, if demonstrated by serial measurements and negative ultrasound, will not be exclusionary, upon communication with and approval from the medical monitor)
 18. Receipt of live vaccines (including attenuated) within 30 days of first study treatment
 19. Women of childbearing potential (WOCBP)*, or sexually active men, who are unwilling to practice highly effective contraception prior to the initial dose/start of the first treatment, during the study, and for at least 6 months after the last dose. Highly effective contraceptive measures include:
 - a. stable use of combined (estrogen and progestogen containing) hormonal contraception (oral, intravaginal, transdermal) or progestogen-only hormonal contraception (oral, injectable, implantable) associated with inhibition of ovulation initiated 2 or more menstrual cycles prior to screening
 - b. intrauterine device (IUD); intrauterine hormone-releasing system (IUS);
 - c. bilateral tubal ligation
 - d. vasectomized partner (provided that the male vasectomized partner is the sole sexual partner of the WOCBP study participant and that the vasectomized partner has obtained medical assessment of surgical success for the procedure)
 - e. and/or sexual abstinence^{†,‡}.
- * WOCBP are defined as women who are fertile following menarche until becoming postmenopausal, unless permanently sterile. Permanent sterilization methods include hysterectomy, bilateral salpingectomy, and bilateral oophorectomy.

A postmenopausal state is defined as no menses for 12 months without an alternative medical cause. A high follicle stimulating hormone (FSH) level in the postmenopausal range may be used to confirm a postmenopausal state in women not using hormonal contraception or hormonal replacement therapy. However, in the absence of 12 months of amenorrhea, a single FSH measurement is insufficient to determine the occurrence of a postmenopausal state. The above definitions are according to Clinical Trial Facilitation Group (CTFG) guidance. Pregnancy testing and contraception are not required for women with documented hysterectomy or tubal ligation.

- † Sexual abstinence is considered a highly effective method only if defined as refraining from heterosexual intercourse during the entire period of risk associated with the study drugs. The reliability of sexual abstinence needs to be evaluated in relation to the duration of the clinical trial and the preferred and usual lifestyle of the patient.
- ‡ Periodic abstinence (calendar, symptothermal, post-ovulation methods), withdrawal (coitus interruptus), spermicides only, and lactational amenorrhoea method (LAM) are

not acceptable methods of contraception. Female condom and male condom should not be used together.

20. Prior treatment with idelalisib

6.3. Premature Withdrawal from the Study

A patient has the right to withdraw from the study at any time, for any reason, and without repercussion.

The investigator and/or sponsor have the right to withdraw a patient from the study if it is no longer in the interest of the patient to continue in the study, or if the patient's continuation in the study places the scientific outcome of the study at risk (eg, if a patient does not or cannot follow study procedures). An excessive rate of withdrawals would render the study uninterpretable; therefore, unnecessary withdrawal of patients should be avoided.

Patients who are withdrawn prematurely from the study will be asked to complete study assessments, as described in Section 8.1.4.

During the treatment period and follow-up period, a patient who withdraws consent to continue participation in the study will not be followed for any reason after consent has been withdrawn.

Rules for discontinuation of study treatment (permanent or temporary) are discussed in Section 7.3.2.

6.4. Replacement of Patients

Patients prematurely discontinued from the study will not be replaced.

7. STUDY TREATMENTS

7.1. Investigational and Reference Treatments

Open-label cemiplimab will be supplied as a liquid in sterile, single-use -vials. Each vial will contain cemiplimab at a concentration of 50 mg/mL. Instructions on dose preparation are provided in the pharmacy manual.

Open-label cemiplimab will be administered in an outpatient setting as an IV infusion over approximately 30 minutes (\pm 10 minutes). Each patient's dose will be administered as a dose of 350 mg Q3W (dose is not weight based, dosing in this study is a flat dose).

A pharmacist or other qualified individual will be identified at each site to prepare cemiplimab for administration. Detailed preparation and administration instructions will be provided to the sites in the pharmacy manual.

7.2. Pretreatment(s)

Appropriate premedication for study treatments may be administered at the investigator's discretion as per usual clinical practice and in accordance with institutional guidelines. No premedications are to be administered for the first dose of cemiplimab.

7.3. Dose Modification and Study Treatment Discontinuation Rules

7.3.1. Dose Modification

The planned dose and schedule is a 350 mg dose of cemiplimab IV over approximately 30 minutes (\pm 10 minutes) Q3W. Patients will generally remain on the assigned dosage of cemiplimab throughout the course of study treatment. Dose reduction of cemiplimab may be allowed following temporary discontinuation of study drug, based on the guidelines below, and only after discussion and agreement between the investigator and sponsor.

7.3.2. Study Treatment Hold or Discontinuation

Patients who permanently discontinue from study drug and who do not withdraw from the study should continue follow-up in the study without additional treatment until progression of disease, completion of all study assessments, or closure of the study (Section 6.3).

Patients who permanently discontinue from study drug and who opt to withdraw from the study will be asked to complete study assessments, per Section 6.3.

Adverse events are to be reported according to the National Cancer Institute Common Terminology Criteria for Adverse Events (NCI-CTCAE) version 4.03. Patients who experience grade ≥ 3 treatment-related toxicity (excluding laboratory abnormalities that are considered clinically insignificant) that is not otherwise specified in the protocol will be required to temporarily discontinue treatment with cemiplimab. Such patients may be considered for resumption of treatment once the toxicity resolves to grade 1 or baseline, or when the toxicity is stable and manageable through supportive/medical therapy (eg, grade 3 hypertension that can be controlled with the addition of a second anti-hypertensive agent).

Upon occurrence of a study treatment-related event at any time in the study, resumption of treatment after resolution or stabilization of the condition is allowed at the discretion of the investigator and sponsor if resuming treatment is thought to be in the best interest of the patient, with the exception of the following categories:

- Patients with events that require cemiplimab to be discontinued for more than 84 consecutive days from the previous dose
- Patients with grade ≥ 2 uveitis will generally be discontinued from study treatment, unless there is resolution to grade ≤ 1 as outlined in [Appendix 3](#) AND discussion with and approval by the medical monitor. All patients with grade ≥ 3 uveitis will be permanently discontinued from study treatment.

After other AEs, resumption of treatment may be at the initial dose level, or at 1 dose level reduced, based upon the discretion of the investigator and the sponsor ([Table 1](#)).

Table 1: Dose Reductions

Dose Level	Reduction Order	Dose
Dose Level -1	First dose reduction	120 mg cemiplimab Q3W
Dose Level -2	Second dose reduction	60 mg cemiplimab Q3W

A patient who requires dose reduction below dose level -2 will be permanently discontinued from the study.

Guidelines for study treatment temporary discontinuations, including delays and interruptions, and permanent discontinuations for toxicity are outlined in [Table 2](#).

Any patient currently receiving cemiplimab who was previously treated with a phosphatidylinositol 3-kinase (PI 3-K) inhibitor and who develops stomatitis or mucositis should temporarily suspend study treatment. If this or any other immune-related AE occurs among these patients, the sponsor should be informed as soon as possible to discuss further management of the patient. An irAE of any grade in a patient previously treated with a PI 3-K inhibitor should be reported as an adverse event of special interest (AESI).

Table 2: Study Treatment Dose Modifications or Discontinuations

Toxicity	Grade	Hold Treatment?	Restarting Criteria	Restarting Dose/Schedule	Discontinuation Criteria
Hematological Toxicity (other than grade 3 thrombocytopenia greater than 7 days or associated with bleeding)	1, 2, 3	No	N/A	N/A	N/A
	4	Yes	Toxicity resolves to grade \leq 1 or baseline	Decrease cemiplimab dosage to the next lower dosing level (see Table 1)	Toxicity does not resolve within 84 days of last infusion Permanent discontinuation should be considered for any severe or life-threatening event
Grade 3 thrombocytopenia greater than 7 days or associated with bleeding	3	Yes	Toxicity resolves to grade \leq 1 or baseline	Decrease cemiplimab dosage to the next lower dosing level (see Table 1)	Toxicity does not resolve within 84 days of last infusion Permanent discontinuation should be considered for any severe or life-threatening event
Nonhematological Toxicity Note: Exceptions to be treated as for Grade 1 toxicity: 
Grade 2 alopeciaGrade 2 fatigueClinically insignificant lab abnormality not meeting AE criteria	1	No	N/A	N/A	N/A
	2	Consider withholding for persistent symptoms	Toxicity resolves to grade 0–1 or baseline	Clinical AE resolves within 4 weeks: Same dose and schedule Clinical AE does not resolve within 4 weeks: May decrease cemiplimab dosage to the next lower dosing level (see Table 1)	Toxicity does not resolve within 84 days of last infusion
	3	Yes	Toxicity resolves to grade 0–1 or baseline	Decrease cemiplimab dosage to the next lower dosing level (see Table 1)	Toxicity does not resolve within 84 days of last infusion
	4	Yes	N/A	N/A	Patient must be discontinued

AE=adverse event, N/A=not applicable

For additional information regarding AEs with a potential for irAEs, reference [Table 3](#) and [Appendix 3](#).

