The first-in-human (FIH) protocol of cemiplimab (R2810-ONC-1423; NCT02383212) evaluates the safety of cemiplimab as monotherapy at different dose levels and in combination with selected other anti-tumor agents that may augment the potency and durability of an anti-tumor immune response. The initial clinical experience with dose escalation cohorts (n = 60 patients) indicates that cemiplimab has generally been well tolerated (Papadopoulos 2016). There were no dose-limiting toxicities (DLTs) in the dose escalation cohorts. The most common treatment-related AEs were fatigue (n=17 [28.3%]), arthralgia (n=7 [11.7%]), and nausea (n=7 [11.7%]). Eight treatment-related AEs of grade ≥ 3 were observed: anemia in 2 cases (3.3%), and 1 (1.7%) case each of lymphopenia, elevated alanine aminotransferase (ALT), elevated aspartate aminotransferase (AST), and cognitive disorder with anti-HuD associated paraneoplastic encephalomyelitis. Objective responses were observed in 18% of patients, including 1 patient with metastatic BCC (see Section 3.2.1). The phase 1 experience supports a 3 mg/kg cemiplimab intravenously (IV) every 2 weeks as dose for further study (see Section 3.2.3).

Libtayo[®] (cemiplimab) has received marketing authorization and is now approved in the United States (US), Europe, Canada, and Brazil for the treatment of patients with metastatic cutaneous squamous cell carcinoma or patients with locally advanced cutaneous squamous cell carcinoma who are not candidates for curative surgery or curative radiation. In the US, it is

approved as cemiplimab-rwlc. The Investigator's Brochure provides further details of nonclinical pharmacology and antitumor activity of cemiplimab.

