7.3.2.1. Immune-Related Adverse Events

Case report forms (CRFs) for this study are designed to capture AEs that may be suggestive of potential irAEs. Attribution of AEs in the CRFs will require not only the investigator's assessment

regarding whether or not the AE was related to cemiplimab, but also whether or not the AE was an irAE. Please see the CRF completion guidelines for information about attribution of irAEs.

Investigators must be extremely vigilant and be ready to intervene early in the management of irAEs, as the onset of symptoms of irAEs (eg, pneumonitis or endocrinopathies) may be subtle. Detailed guidance of management of irAEs is provided in [Appendix 3](#). In the event of irAEs that are not addressed in [Appendix 3](#), general guidance is provided in [Table 3](#). The recommendations in [Table 3](#) and [Appendix 3](#) should be seen as guidelines, and the treating physician should exercise clinical judgment based on the symptoms and condition of the individual patient.

Table 3: General Treatment Hold Guidelines for Immune-Related Adverse Events

Severity	Withhold/Discontinue Treatment?	Supportive Care
Grade 1	No action	Provide symptomatic treatment
Grade 2	May withhold treatment	Consider systemic corticosteroids in addition to appropriate symptomatic treatment
Grade 3 Grade 4	Withhold treatment Discontinue if unable to reduce corticosteroid dose to <10 mg per day prednisone equivalent within 12 weeks of toxicity	Systemic corticosteroids are indicated in addition to appropriate symptomatic treatment. May utilize 1 to 2 mg/kg prednisone or equivalent per day. Steroid taper should be considered once symptoms improve to Grade 1 or less and tapered over at least 4 weeks. For any severe (Grade 3-4) irAE, if symptoms worsen or do not improve on adequate corticosteroids within 48 to 72 hours, consider adding additional immunosuppressive agents (to be selected from agents such as infliximab, cyclophosphamide, cyclosporine, mycophenolate mofetil). Referral of the patient to a specialized unit for assessment and treatment should be considered.

Note: These recommendations should be seen as guidelines, and the treating physician should exercise clinical judgment based on the symptoms and condition of the individual patient.

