	Grade 3–4	Hold (and consider discontinuation of) cemiplimab when AST or ALT >5.0 times ULN and/or total bilirubin >3.0 times ULN.	
 Consider appropriate consultation and liver biopsy to establish etiology of hepatic injury, if necessary. Treat with high-dose IV glucocorticosteroids for 24–48 hours. When symptoms improve to grade 1 or less, a steroid taper with dexamethasone 4 mg every 4 hours or prednisone at 1–2 mg/kg should be started and continued over no less than 4 weeks. If serum transaminase levels do not decrease 48 hours after initiation of systemic steroids, oral mycophenolate mofetil 500 mg every 12 hours may be given. Infliximab is not recommended due to its potential for hepatotoxicity^b. Several courses of steroid tapering may be necessary as symptoms may worsen when the steroid dose is decreased. 		
Nausea	≤Grade 1	No change in dose	
 Nausea should be treated aggressively, and consideration should be given in subsequent cycles to the administration of prophylactic antiemetic therapy according to standard institutional practice. Patients should be strongly encouraged to maintain liberal oral fluid intake. 		
	Grade 2	Hold until ≤Grade 1. Resume at same dose level. May increase dosing interval by 1 week if it takes more than 4 weeks for toxicities to resolve.			
	Grade 3	Hold until <Grade 2. May increase dosing interval by 1 week for each occurrence. Discontinue if toxicities do not resolve within 12 weeks.			
	Grade 4	Off protocol therapy			

Event(s)	CTCAE v4.03 Grade	Management/ cemiplimab Dosing	Action/Supportive Care Guidelines	Symptoms ^a	Differential Diagnosis
Neutropenia	≤Grade 1	No change in dose	For neutropenia, see general guidelines on hematologic toxicity in Table 2		
	Grade 2	No change in dose			
	Grade 3	No change in dose			
	Grade 4	See Table 2			

Event(s)	CTCAE v4.03 Grade	Management/ cemiplimab Dosing	Action/Supportive Care Guidelines	Symptoms ^a	Differential Diagnosis

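### For Grade 3 immune-related hematologic events that Appendix 3 does not list, Table 2 says not to hold cemiplimab, Table 3 says to withhold it, and no text says which table governs

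*Protocol*

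**What the plan says.** Protocol Section 7.3.2 introduces Table 2 with the words "Guidelines for study treatment temporary discontinuations, including delays and interruptions, and permanent discontinuations for toxicity are outlined in" that table. The first row, "Hematological Toxicity (other than grade 3 thrombocytopenia greater than 7 days or associated with bleeding"), answers no to holding treatment at Grades 1, 2 and 3 and yes at Grade 4. The thrombocytopenia excepted in the row label has its own row, which calls for a hold. Nothing in either row depends on whether the event is immune-related.

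Directly after Table 2 comes one linking sentence: "For additional information regarding AEs with a potential for irAEs, reference [Table 3](#) and [Appendix 3".

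Section 7.3.2.1 then sets an order between the two sources of irAE guidance: "In the event of irAEs that are not addressed in [Appendix 3](#), general guidance is provided in [Table 3". For Grade 3 and Grade 4 irAEs, Table 3 reads: "Withhold treatment Discontinue if unable to reduce corticosteroid dose to <10 mg per day prednisone equivalent within 12 weeks of toxicity". Its supportive-care column adds: "Systemic corticosteroids are indicated in addition to appropriate symptomatic treatment". Table 3 has no exception for hematologic events.

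Appendix 3 has two hematologic rows. For neutropenia it gives no dose change at Grade 3 and says "For neutropenia, see general guidelines on hematologic toxicity in Table 2". For thrombocytopenia it refers Grades 3 and 4 to Table 2. It has no row for anemia, hemolysis, lymphopenia or any other hematologic event.

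**The concern.** An event can be both a hematologic toxicity and an irAE. Table 2 classifies by organ system and Table 3 by attributed cause, and neither excludes the other's territory. Where Appendix 3 does not step in, a site that reads Table 2 continues infusions and a site that reads Table 3 withholds them, for the same event at the same grade.

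First at stake is patient safety: two opposite written instructions for a severe event, in a study planned for up to about 70 sites (Section 6.1). Second is consistency of the safety and exposure summaries. Whether a dose is held feeds directly into actual and relative dose intensity (SAP Section 5.7).

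**Working it through.** No calculation applies. The check traces each kind of Grade 3 hematologic event, once attributed as immune-related, through the order of reference the protocol sets.

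| Grade 3 event judged an irAE | Appendix 3 | Table 2 hold | Table 3 reached? | Conflict on the hold |
|---|---|---|---|---|
| Neutropenia | No dose change; refers to Table 2 | No | No, because Appendix 3 addresses it | None |
| Thrombocytopenia, 7 days or less and no bleeding | Refers to Table 2 | No | No | None |
| Thrombocytopenia, over 7 days or with bleeding | Refers to Table 2 | Yes | No; Table 3 would also withhold | None |
| Any other hematologic event (for example anemia, hemolysis, lymphopenia) | No row | No | Yes: withhold | Yes |

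Only the last line conflicts. Next, does any text break the tie?

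1. The linking sentence after Table 2 sends potential irAEs to Table 3 and Appendix 3 for additional information. It does not say that they replace Table 2.
2. The ordering sentence in Section 7.3.2.1 ranks Appendix 3 ahead of Table 3. It does not rank Table 3 against Table 2.
3. Section 7.3.2 has a default that requires a hold for treatment-related toxicity of Grade 3 or higher, but only where the protocol specifies nothing else. Here both tables specify an action, so the default does not decide between them.
4. Section 7.3.2.1 describes Table 3 and Appendix 3 as guidelines subject to clinical judgment, and Section 7.3.2 calls Table 2 guidelines too. The two tables have the same standing.

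None of the four gives precedence.

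Other grades: at Grade 4 both tables hold. At Grade 2, Table 3 only permits a hold, so not holding satisfies both. The contradiction is therefore confined to Grade 3.

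Table 3 is read here as one joint row for Grades 3 and 4. If the original layout assigned the withholding instruction to Grade 3 and the discontinuation instruction to Grade 4, the Grade 3 result would be the same.

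The events in the last line are of a kind the study would see. Hemoglobin and lymphocytes are in the hematology panel (Section 8.2.3.6), which is drawn at every dosing visit (Tables 4 and 5). The first-in-human experience in Section 1.2 lists, among treatment-related events of Grade 3 or higher, "anemia in 2 cases (3.3%), and 1 (1.7%) case each of lymphopenia".

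**The case against.** The best answer is that a natural reading exists. Table 2 is the general toxicity table, the sentence after it directs potential irAEs to Table 3 and Appendix 3, and investigators must record whether each event is an irAE. A physician who makes that attribution would reasonably turn to the irAE table. That reading is plausible, but it is an inference: the link is worded as extra information, and the two Appendix 3 cytopenia rows point the other way, to Table 2. A site could as reasonably conclude that Table 2 covers all cytopenias.

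The protocol also has safeguards. Irrespective of the table followed, Grade 3 or greater irAEs are listed among the adverse events of special interest, to be reported to the sponsor within 24 hours (Section 9.4.3). The medical monitor must be consulted about significant laboratory abnormalities that do not resolve or are not explained by causes other than study drug (Section 8.2.3.6). Study drug may be stopped for any condition that jeopardizes safety (Section 7.3.2.2). These make it less likely that divergent handling goes unnoticed. They act after the site has already had to choose between two instructions, so they soften the consequence without removing the contradiction.

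A reader might infer more than the documents support:

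- *That every Grade 3 immune-related hematologic event is in conflict.* It is not; Appendix 3 resolves neutropenia and thrombocytopenia.
- *That Grade 2 is also contradictory.* A permission to withhold is compatible with not holding.
- *That the tables conflict on corticosteroids.* Table 2 is silent on them, so a site can follow Table 3 on steroids whatever it does about the hold.
- *That the count of identified irAEs will depend on the table read.* SAP Section 4.5.2 counts treatment-related events on a sponsor list of preferred terms that need corticosteroids or immunosuppressants, or are endocrinopathies. The list is not in the documents, and Table 2 does not bar steroids.

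**Conclusion.** The contradiction stands in a narrow form. For Grade 3 hematologic events attributed as immune-related, other than neutropenia and thrombocytopenia, Tables 2 and 3 give opposite hold instructions and no text says which prevails.

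Its size in patients cannot be stated. It is tempting to take the 3 first-in-human events among 60 patients (3/60 = 5.0%; exact 95% CI 1.0% to 13.9%, if one per patient) and scale to 137 patients (0.05 × 137 = 6.9; 0.139 × 137 = 19.0). Those figures do not measure this problem. Section 1.2 does not describe the anemia or lymphopenia as immune-related. The events are of Grade 3 or higher, and any at Grade 4 would be held under both tables. The patients came from dose-escalation cohorts in another study.

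The ORR test, its alpha and its power are not affected. The matter is one of patient safety and uniform conduct, with a secondary effect on dose-intensity summaries. The conclusion assumes that the tables as extracted carry their full text, and that an event may be attributed as an irAE while remaining a hematologic toxicity, which nothing in the protocol excludes.

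**What to change.** The sponsor must reconcile the hold instructions of Tables 2 and 3 for Grade 3 hematologic events attributed as immune-related and not listed in Appendix 3. The protocol should then say which table governs, in two places: a footnote to the hematologic row of Table 2 and a sentence in Section 7.3.2.1. Which instruction applies is for the sponsor's clinicians to decide; this review takes no position on it.

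No procedure, visit, sample or analysis is added. The cost is one footnote and one cross-reference sentence, made through a protocol amendment and communicated to sites.
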